3) For *anti*-3-¹⁸F]FACBC, uptake will be defined according to the following criteria in relation to background structures: mild (above blood pool but less than marrow), moderate (above or equal to marrow but less than liver), and intense (equal to or above liver). Visual analysis will be aided by quantitative criteria of SUV_{max} lesion/SUV_{mean} background. Maximum and mean SUV of each focus of abnormal uptake as well as background structures including liver, marrow at L3, aorta, and bladder will be recorded. For prostate beds as well as extra-prostatic sites such as lymph nodes and bone, abnormal moderate or intense focal uptake over background marrow which persist from early to delayed images will be considered prospectively positive. These criteria were used to analyze data in our study of *anti*-¹⁸F]FACBC in recurrent disease [40].

4) Confidence in interpretation for disease within the prostate bed and outside the bed will be recorded with the following scale on a per patient basis and any all recordable lymph nodes: 1- definitively negative; 2 -probably negative; 3 - indeterminate; 4 - probably positive; 5 – definitively positive.

5) In summary, we will record both visual and semi-quantitative analysis of the prostate bed, positive lymph nodes (greater than blood pool), and other structures such as skeletal foci on early and delayed time frames. We will use maximum and mean SUV as well as standard bidimensional size measurements. We will also record similar measurements on background structures such that we may derive uptake ratios.

C1.5 Image Analysis of MR

The MR studies will be interpreted by an MR imager. (At some point after primary analysis, a 2nd interpretation may also be blindly performed and agreement (Z Value) recorded.) Studies will be interpreted utilizing standard interpretative criteria for MR and including anatomic criteria, perfusion analysis and DWMR criteria. Confidence in interpretation for disease within the prostate bed and outside the bed will be recorded for each of these three interpretative categories individually and in aggregate with the following scale on a per patient basis and any all recordable lymph nodes: 1-defiinitvely negative; 2 -probably negative; 3 - indeterminate; 4 - probably positive; 5 – definitively positive. Typically, a combination of abnormality on all relevant sequences will result in a “5” (e.g. DCE, DWI, and T2), while no abnormality on any sequence will result in a “1”. A combination of suspicious and benign findings on pulse sequences will result in a “2”, “3”, or “4” depending on particular findings.

C1.6 Image Analysis of PET-MR

After individual interpretation of each study, then the PET and appropriate sequences from the MR (typically post-contrast abdominopelvic supplemented by other sequences) will be co-registered using rigid software registration on a MimVista 5.5 or similar workstation. The studies will then be analyzed by consensus by one of the 2 nuclear imagers and the primary research MR imager. All foci previously recorded by each group as positive or negative will then be assessed by the group taking into account all parameters previously employed. New foci may also be identified. Confidence in interpretation for disease within the prostate bed and outside the bed will then be recorded with the following scale on a per patient basis and any all recordable lymph nodes: 1-defiinitvely negative; 2 -probably negative; 3 - indeterminate; 4 - probably positive; 5 – definitively positive. Typically agreement on both studies will be recorded

as “1” or “5”, and combination of lack of agreement in a “2”, “3”, or “4” depending on particular findings.

C1.7 Clinical and Histologic Assessment.

Methods. After the *anti*-[¹⁸F]FACBC scan has been obtained and interpreted, the following will occur:

- 4) All patients may also be followed up as scientifically appropriate at least one year and up to five years regardless of initial findings in order to optimize correlation of imaging to clinical findings. It is not possible to do a template nodal dissection on all patients regardless of findings, and certainly not on nodal imaging negative patients. While it is true that we will not biopsy lymph nodes if all the imaging modalities are negative, there will be patients who are MR imaging positive but PET negative and visa-versa who will get biopsied. Yet biopsies or sampling will typically performed only when there is an identifiable target on anatomic imaging and will thus be standard of care. Some patients who undergo open or laparoscopic nodal sampling for positive findings will have a limited template dissection of adjacent imaging negative nodes (a standard practice). By clinical and ethical necessity, the imaging and biopsy negative patients will be confirmed by lack of lymph node progression on imaging as well as stable PSA levels. The standard of care outside the trial includes serial PSA measures as well as appropriate imaging such as CT or MR and repeat imaging as required.
- 5) A Ground Truth Panel composed of two urologists ([name] and [name] or substitute) and a radiation oncologist ([name] or substitute) will meet once sufficient data has been collected and/or communicated via email. The diagnostic imagers will not be included on this panel but will present the data. Truth will be ascertained via the criteria outlined below. If there were initial differences of opinion, further discussion will ensue until a group consensus can be achieved.

6) Presence or absence of disease in the prostate bed will be confirmed by biopsy only overridden by clinical data. For example, a substantial reduction in PSA after prostatic bed salvage therapy without a subsequent substantial PSA rise in at least 6 months would not only establish presence of presumed prostatic bed disease but also absence of extraprostatic disease. Extraprostatic nodal involvement per patient will be typically confirmed by pathologic proof or under certain circumstances by response after focal therapy if scientifically justifiable. Skeletal involvement will be confirmed with either biopsy or typical appearance on MR [41] or other accepted confirmatory imaging such as typical appearance on bone scan or CT. Absence of extraprostatic disease will typically be confirmed by either a substantial reduction in PSA after prostatic bed therapy without a substantial rise in at least 6 months as above, and/or stable appearance on CT or MRI for greater than 1 year without evidence of nodal or bone involvement as medically and scientifically appropriate. Because some patients had definitive follow-up for the prostate bed but not extraprostatic disease, and visa-versa, the number of patients in each sub-analysis may differ.

7) Patients who are prostate bed positive and extraprostatic negative may get treated with local therapy (radiation, cryoablation, salvage surgery, etc.) as appropriate. Most of these patients will not initially get hormonal therapy and will be entered into the followup group. It is true that some patients with either high Gleason scores, impending or with cord compression and/or pathologic fracture, hydronephrosis, and/or rapid PSA doubling time of less than 3 months will require hormonal therapy, but this is not the majority of patients (approximately 15-20% worst case scenario). The majority of patients (80-85%) will have low to intermediate risk disease and PSA recurrence reflecting the prevalence of low and intermediate risk disease in the United States. Therefore these patients can be followed off hormonal therapy but with local therapy as needed.

C1.8 Correlation of FACBC and MR to and Clinical Outcome

Upon completion of the study and/or after additional follow-up, each patient may be re-reviewed by the same Ground Truth Panel to determine if the predicted findings on *anti*-[¹⁸F]FACBC scan and MR individually and in tandem match those of clinical and pathologic findings especially in regard to the identification of prostatic versus extraprostatic recurrence. Also at that time uptake parameters will be reviewed. At no time this study will interfere with proper therapy as determined by the patient's physicians and the patient.

C2.0 Study Design and Methods (Aim2 and Sub Aim 2a)

Rationale. We hypothesize that *anti*-[¹⁸F]FACBC uptake is mediated by a LAT protein subtype or subtypes. However, the precise LAT subtype involved in all cases is unknown. We also further hypothesize that there are genotypic differences between recurrent prostate carcinoma cells confined to the prostate bed and those that are extraprostatic and that these differences can be explored via proper identification of candidate tissue via transmolecular imaging to be performed at termination of study or when sufficient tissue has been collected.

Experimental Design. To test the above hypothesis, we will compare mRNA expression of recurrent prostate carcinoma tissue within the prostate bed and extraprostatic. In addition we will utilize *anti*-[¹⁸F]FACBC avid tissue to confirm that the following AAT subtypes based on preliminary data are expressed at the protein level: PAT 1, LAT1, LAT2, 4F2hc, and ASCT2, LAT3 and ASCT1. We will study 8-10 samples of each recurrent prostate carcinoma in the prostate bed and 8-10 samples of disease outside the prostate bed, preferably in the same patient. We predict that one or more AAT subtypes will be relatively overexpressed by IHC in FACBC-avid carcinoma. We also predict that there will be differences in mRNA expression

based on these tissue samples between disease confined to the prostate bed and those that are extraprostatic. Based upon tissue availability we will perform IHC in the following rank priority: First: PAT 1; Second: LAT1, LAT2, 4F2hc; Third: ASCT2, LAT3 and ASCT1. This priority ranking is based on our desire to first confirm phenotypic expression of PAT1, since presence of this AAT correlated most strongly with *anti*-[¹⁸F]FACBC uptake, followed by LAT1 and LAT2 with the heterodimeric associated protein 4F2hc, and ASCT2, LAT3 and ASCT1.

C 2.1 Quantitative next-generation mRNA sequencing

Methods. For experiments on fixed tissue RNA will be extracted at the Cancer Genomics Shared Resource (CGSR) at the Winship Cancer Institute from macrodissected 5 micron sections. The CGSR has extensive experience in preparing Total RNA from FFPE tissues [42]. FFPE RNA extraction will be performed using the Omega Biotech methodology in 96-well format on a Kingfisher FLEX Liquid Handler Robot. FFPE RNA will be quantitated by nanodrop spectrophotometry, and tested for RNA integrity and quality by Taqman analysis of the RPL13a ribosomal protein. Samples with sufficient yield (>500 ng), A_{260}/A_{280} ratio > 1.8 and RPL13a C_T values less than 31 cycles will be used for preparing sequencing libraries using the TrueScript kit (Illumina). Amplified cDNA libraries will be sonicated to an average length of 250 bp with a Covaris E-120 Adaptive Focused Acoustics Instrument. We will repair the ends of the sonicated DNA using the Illumina TrueScript protocol and generate barcoded libraries for RNA-seq analysis on an Illumina HiSeq 2000 instrument at the Southern California Genotyping Consortium at UCLA. Agilent Bioanalyzer Nanochip analysis will be performed to ensure the integrity of libraries prior to sequencing. We will obtain 60 million reads per sample of 50bp paired-end sequencing reads using the Illumina version 3 kits with three samples multiplexed per sequencing lane.

Fluorogenic quantitative RT-PCR assays will be used to confirm changes identified by RNA-seq analysis and performed in triplicate with standard SYBR-Green methodology on the I-cycler system (Bio-Rad, Hercules, CA, USA) according to published protocols with minor modifications [43]. Reaction specificity will be assessed by melting point analyses, in which single melting point peaks are required at temperatures predicted by amplicon sequence. Reactions without reverse transcription and template will serve as controls for DNA contamination and specimen carry-over. Test gene expression will be normalized to 28S ribosomal RNA and referenced to a standard RNA specimen. Relative normalized gene expression of each LAT subtype will be compared in FACBC avid versus non-avid prostate carcinoma, with statistical significance assessed by analysis of variance (ANOVA).

C 2.2 Immunohistochemistry

Methods. Fixed tissue sections (5 μ m thickness) will be dewaxed, and steam antigen retrieval will be performed at pH 6.5 in a pressure cooker for 20 minutes [44]. Tissue sections will be incubated with primary antibodies directed against PAT 1, LAT1, LAT2, 4F2hc, and ASCT2, LAT3 and ASCT1. Sections will be deparaffinized and subjected to heat-induced epitope retrieval by steaming for 15 minutes. IHC staining will be performed at the Winship Cancer Institute Research Pathology Shared Resource using an automated (DAKO) immunohistochemistry stainer and established procedures and protocols. Optimal dilutions for all antibodies will be determined empirically using archived sections from prostatectomies and blocking reagents recommended by the manufacturers. Immunohistochemical reactions will be developed with diaminobenzidine as the chromogenic peroxidase substrate. Sections will be counterstained with hematoxylin after immunohistochemistry. Specificity will be verified by negative control reactions without primary antibody. Intensity of the various immunohistochemical stains were scored blindly by a board-certified pathologist as follows; 0-

negative, 1+ (weak), 2+ (intermediate) and 3+ (strong). The expression of these markers will be correlated with FACBC uptake by ANOVA testing

C 2.3 RNA-Seq Results and Imaging Findings

RNA-Seq sequencing reads produced from the Illumina HiSeq 2000 will be mapped to the human reference genome (hg19) using Bowtie [45] and fragment reads per kilobase (FRPK) calculated using TopHat [46]. Only uniquely mapped reads will be retained for analysis. Relative changes in mRNA expression will be computed using Cufflinks and Cuffdiff [47] in a locally installed Galaxy bioinformatics environment [48, 49] deployed by the [name] laboratory.

D. Subject recruitment:

All patients will be recruited from the Emory Healthcare (Drs. [name], [name], [name] and [name]), Urology and Radiation Oncology clinics per the inclusion and exclusion criteria below.

Inclusion Criteria:

1. Patients must be 18 years of age or older.
2. Patients will have been originally diagnosed with localized (Stage T1c, T2, or T3) prostate carcinoma and have undergone what was considered definitive non-prostatectomy therapy for localized disease.
3. In the case of cryotherapy, external beam radiation, or HIFU the procedure will have occurred at least one year in the past. In the case of brachytherapy, treatment will have occurred at least 2 years in the past to eliminate patients with so-called "PSA bump."
4. Patient will have suspicion of recurrent prostate carcinoma as defined by: the ASTRO-RTOG Phoenix criteria of elevated PSA greater than nadir plus 2 ng/ml with absolute PSA \geq 4.0 ng/ml with any doubling time (DT) or with PSA 2.0-3.99 ng/ml with DT \leq 10 months.
5. Ability to lie still for PET scanning
6. Patients must be able to provide written informed consent.

Exclusion Criteria:

1. Age less than 18.
2. Greater than T3 disease in past and/or treated with prostatectomy.
3. Less than 1 year since cryotherapy, external beam radiation therapy, or HIFU, or 2 years since brachytherapy.
4. Does not meet above criteria of suspicious PSA elevation
5. Inability to lie still for PET scanning
6. Cannot provide written informed consent.
7. Bone scan findings characteristic for metastatic prostate carcinoma
8. Less than 1 month since any prior prostate biopsy (to decrease false positive uptake from inflammation).

Written informed consent will be obtained before subject participation in the study. No procedures will be performed before written informed consent is obtained. Participants will be assigned an identification number for screening purposes; data collected during the screening process will be recorded using that number.

PET Scan Day: The following procedures will be performed:

- Obtain written informed consent
- Inclusion/exclusion criteria review
- Vital signs measurements
- Clinical laboratory tests (serum chemistries, CBC and urinalysis)
 - To be repeated at one week (+/- 3 days) after scan

E. Statistical Analysis

E.1 Aim 1

Receiver Operating Characteristic (ROC) analysis will be conducted to instigate the predictive power of FACBC PET and MR and determine if a variation in standard criteria or if combined criteria better maximizes sensitivity, specificity and accuracy of *each technique* using Chi-square test. The predictive accuracy of each technique will be determined using the positive predictive value (PPV) relative to the clinical and pathologic findings. The PPV of imaging will be assessed by calculating the probability of obtaining clinical and pathological outcomes that confirm the predicted positive findings based on the individual and combined scans. A similar negative predictive value (NPV) will also be calculated based upon a negative pathologic sampling as well as clinical/imaging follow-up at least 1 year or more. Formal hypothesis testing will be conducted to obtain inferences regarding differences between the predictive accuracies of these two approaches.

Each case will be evaluated as follows:

- 1) Results of biopsy as well as clinical follow-up will be correlated with prediction of local and distant neoplastic involvement by MR and *anti*-[¹⁸F]FACBC PET-CT.
- 2) Results of biopsy of lymph nodes or other extra-prostatic sites as well as clinical follow-up will be correlated with prediction of extraprostatic neoplasia by MR and *anti*-[¹⁸F]FACBC PET-CT.
- 3) Registered PET and MR will be correlated both qualitatively and quantitatively to pathologic and clinical results and in the discrimination of prostatic from extra-prostatic recurrence.
- 4) **Thus, truth for presence of disease will be established by biopsy/pathology and/or appropriate clinical followup. Truth for absence of disease will be established via pathologic sampling as well as standard clinical follow-up for at least 6 months and up to five years. We believe there will be enough patients with biopsy and clinically followed-up negative lymph nodes to calculate a true negativity rate.**

E2.0 Secondary Aims

Aim 2. and Sub-aim 2a.

Depending on the normality of data distribution, t-test or Wilcoxon rank sum test will be conducted to compare the mRNA differences, genomic differences in gene expression, alternative splicing, indels and single base mutations between prostate carcinoma recurrent in the prostate bed and extraprostatic samples. Analysis of variance (ANOVA) will be used to compare the IHC staining of protein levels between the different categories of FACBC uptake. Tukey pairwise comparison will be further conducted when the overall comparison with ANOVA

Version 9-23-13

Version 11-6-13

Version 11-11-14

Version 12-4-14

is significant at the significance level of 0.05. Pearson/Spearman correlation coefficients will be estimated to measure the associations: 1) between mRNA levels of candidate AAT genes and FACBC uptake; 2) between mRNA differences and quantifiable imaging biomarker data such as SUV for *anti*-[¹⁸F]FACBC PET-CT and ADC for MR. Multivariate analyses will further be conducted, in which general linear model (GLM) will be employed to assess the adjusted relationships mentioned above after adjusting for the other covariates.

Sample size and power calculation

The sample size of this study is 25 patients. The power calculation is based on the comparison of mRNA differences between the prostate bed and extraprostatic samples using two sided t-test. At the significance level of 0.05, the sample size of 25 will achieve a power of at least 80% to detect one standard deviation or higher difference in mRNA difference between the two groups of samples.

F. Adverse Event Reporting

An adverse event is defined as any untoward medical occurrence associated with the use of a drug in humans whether or not considered drug-related

A significant shift from baseline which can be attributable to the radiotracer injection and not the patient's medical condition will be considered an unexpected AE. An event greater than 7 days post scan will not be considered an AE since 95% of ligand is eliminated by 7days.

The National Cancer Institute's Common Terminology Criteria for Adverse Events (CTCAE) Version 4.03 (June 14, 2010) will be used as a guide address potential AEs subject to limitations above and medical and scientific judgment as to plausibility of such criteria in a diagnostic radiotracer study.

Adverse Event Reporting

Any patient death that may be due to the study procedure (i.e. severe radiotracer reaction), unanticipated problem, would be promptly reported to the Emory IRB office. Additionally any patient death not associated with the study procedure or serious unanticipated event(s) (i.e. radiotracer allergy) will be reported to the Emory IRB and FDA upon continuing review. Protocol deviation/non-compliance will be reported according to IRB Policies & Procedures. This radiotracer is studied under IND 72437 and monitoring will be performed per already agreed upon FDA guidance. Over 900 patients in multiple centers have been studied without adverse events.

G. Safety Monitoring

This study is being performed under the auspices of FDA IND 72,437. Patients will be monitored by the technologists and study nurse before and after the studies for any adverse events/reactions. They will be given contact phone numbers to call if they experience any problems (i.e. problems with the IV site, any allergic reaction symptoms). They will be followed routinely by their referring physician with clinical exams, and the PI will work with the co-investigators and referring physicians to ensure that the patients continue to follow up as

scheduled. In addition, a DSMB who will consist of Drs. [name], [name], [name], and [name] will meet formally if a drug related serious adverse event has been reported.

Patient safety, study efficacy and compliance will be reviewed at the Urology working group meeting. The Data and Safety Monitoring Committee (DSMC) of the Winship Cancer Institute will also oversee the conduct of this study (every 6 months or annually – depending on the risk level of the protocol). This committee will review pertinent aspects of study conduct including patient safety, compliance with protocol, data collection and efficacy. The committee will review the charts of 10% of patients enrolled to the study and two of the first 5 patients entered to the study. The Committee reserves the right to conduct additional audits if necessary. The Principal Investigator (PI) or designee is responsible for notifying the DSMC about the accrual of patients when the first 5 have been entered to the study. The PI or designee will also notify the DSMC of study status within 2 months before the next scheduled review is due.

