Our rationale for utilizing patients with PSA ≥ 4 is as follows. A total of 127 patients have been studied already in an R-01 study of the diagnostic performance of *anti*-3-[¹⁸F]FACBC versus conventional imaging. If the patients are stratified by PSA level as in the table below, 41/73 were positive in the prostate bed only, 25 in both prostate bed and lymph nodes, and 1 in lymph nodes only. Thus, in the 25 patients whom will be studied in this population,

approximately 23 will be expected to have disease in the prostate bed and approximately 9 will have disease in nodes, most of the latter will also have disease in the prostate bed. This should provide sufficient tissue for the above secondary aims. In addition, we have demonstrated that greater extraprostatic involvement will occur with shorter DT even at lower PSA levels. Thus the addition of PSA 2.0-3.99 ng/ml plus DT \leq 10 months is a reasonable method to increase recruitment while still acquiring tissue from extraprostatic involvement.

PSA group	<4 (n=54)	\geq 4 (n=73)	Total(n=127)
Prostate bed only (+)	27	41	68
LN only (+)	3	1	4
Both	8	25	33
Total	38	67	105

We hypothesize that by identification of disease recurrence in the prostate bed and extra-prostatic locations, we can exploit differences in mRNA analysis to correlate these differences to synthetic amino acid transport as well as MR parameters such as ADC mapping, and also better understand the relationship of AAT protein expression to *anti*-3- ^{18}F FACBC uptake. **Therefore the most comprehensive manner to obtain tissue to test our hypotheses is within the context of this prospective clinical trial.**

[figure not shown]
C1.0 Research Design and Methods (Aim 1)

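### Leaving out men whose nodal truth is unsettled is expected to overstate extraprostatic sensitivity for MR and for either scan positive, and the plan has no rule, count or bounds for them

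*Combined protocol and SAP*

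**What the plan says.** Aim 1 covers extraprostatic as well as local recurrence. E.1 plans sensitivity, specificity, accuracy, PPV and NPV for the scans singly and combined, with a formal comparison. Truth for extraprostatic disease is set mainly in C1.7:

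- **Sampling (items 2 and 4).** Suspicious sites may be sampled as clinically appropriate. Men positive on one scan only are to be biopsied, but "biopsies or sampling will typically performed only when there is an identifiable target on anatomic imaging". For the rest, "we will not biopsy lymph nodes if all the imaging modalities are negative".
- **Scan-negative men (item 4).** "the imaging and biopsy negative patients will be confirmed by lack of lymph node progression on imaging as well as stable PSA levels".
- **Presence (item 6).** Nodal disease is typically settled by pathology, or in some circumstances by response to focal therapy.
- **Absence (item 6).** This rests on a PSA fall after prostate-bed therapy that holds for at least 6 months, and/or CT or MRI that is stable for more than a year.
- **Denominators (item 6).** "some patients had definitive follow-up for the prostate bed but not extraprostatic disease", and the reverse also occurs, so "the number of patients in each sub-analysis may differ".

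Follow-up of one to five years is permitted whatever the scans show. C1.8 allows the Ground Truth Panel to review cases again, and E.1 lets clinical follow-up establish presence. No section says how a man with unsettled extraprostatic truth is handled. None plans bounds or an adjustment for verification that depends on the scan result.

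**The concern.** Whether a man's nodal status gets settled depends on the scans being evaluated. A man with a node that both scans missed has no target to sample. Under C1.7 he will probably be called negative, or meet no criterion and drop out. Either outcome removes a false negative from the sensitivity denominator. He counts as a miss only if later follow-up proves disease. E.1 allows that, but no section defines when nodal progression makes the baseline scan a false negative, and follow-up is optional.

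Extraprostatic detection is a core Aim 1 result, and the Background says the data may be used to design a larger study. A sensitivity that is too high would carry forward. Without a count of unsettled men by scan result, a reader could not judge by how much.

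**Working it through.** **1. The plan's own counts.** "The sample size of this study is 25 patients". In the earlier series, the PSA ≥ 4 group (n = 73) had "25 in both prostate bed and lymph nodes, and 1 in lymph nodes only", and 41 positive in the bed only.
- Nodes: 25 × (25 + 1)/73 = 8.90
- Bed: 25 × (41 + 25)/73 = 22.60

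These reproduce the stated expectation that "approximately 23 will be expected to have disease in the prostate bed and approximately 9 will have disease in nodes". The sensitivity denominator is therefore about 9 men.

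**2. Either scan positive.** Let Se be the true sensitivity. Let v1 be the share of node-positive men settled as positive when a scan is positive, and v0 the share when both are negative. Then

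apparent Se = Se·v1 / [Se·v1 + (1 − Se)·v0].

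There is no bias if v0 = v1, and upward bias if v0 < v1. The documents give neither share, so v1 = 0.9 and the v0 values are assumptions. The value 0.86 is borrowed, as an illustration only, from the diffusion-weighted MR nodal study cited in the Background.

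| True Se | v0 = 0.50 | v0 = 0.25 | v0 = 0 |
|---|---|---|---|
| 0.70 | 0.81 | 0.89 | 1.00 |
| 0.80 | 0.88 | 0.94 | 1.00 |
| 0.86 | 0.92 | 0.96 | 1.00 |

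At Se = 0.86, 9 × 0.14 = 1.3 men are missed by both scans on average, and the chance of at least one is 1 − 0.86⁹ = 74%. At Se = 0.70 the figures are 2.7 men and 96%.

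**3. In counts.** Take 9 node-positive men, 7 detected and 2 missed. Sensitivity is 7/9 = 78% if both misses are settled, 7/8 = 88% if one is lost, and 7/7 = 100% if both are.

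**4. Each scan alone.** Assume PET 0.70 and MR 0.50, independent. The shares of node-positive men are 0.35 both positive, 0.35 PET only, 0.15 MR only and 0.15 neither.
- Any-positive men settled equally, neither-positive men not at all: PET 0.70/0.85 = 0.82, MR 0.50/0.85 = 0.59.
- Both-positive and MR-only settled 90%, PET-only 45% (no anatomic target), neither-positive 50%: the settled shares are 0.315, 0.135, 0.1575 and 0.075, total 0.6825. PET appears as 0.4725/0.6825 = 0.69, slightly below the truth. MR appears as 0.45/0.6825 = 0.66 and either-positive as 0.6075/0.6825 = 0.89 (truth 0.85), both too high.

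The MR direction is the firmer one. Poor settling of PET-only men takes misses out of MR's denominator, but takes detections away from PET.

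**5. NPV.** Assume PET 0.80, MR 0.60, specificity 0.85 for both, independence, and prevalence 9/25 = 0.36.
- True PET NPV: 0.64 × 0.85 = 0.544 true negatives and 0.36 × 0.20 = 0.072 false negatives; 0.544/0.616 = 88%.
- All double-negative men dropped: 0.544 × 0.15 = 0.0816 and 0.072 × 0.60 = 0.0432; 0.0816/0.1248 = 65%.
- Double-negative missed nodes called negative: 0.072 × 0.40 = 0.0288 moves across; 0.5728/0.616 = 93%.

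**6. A PET/MR ratio among men positive on at least one scan.** At 0.80 and 0.60 the ratio of true-positive rates is 0.80/0.60 = 1.33. If PET-only men are settled 50% and other scan-positive men 90%, it is (0.432 + 0.160)/(0.432 + 0.108) = 1.10. Expected discordant node-positive men: 9 × (0.32 + 0.12) = 4.0.

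**The case against.** The plan is open about not biopsying scan-negative nodes, and doing so would be neither practical nor ethical. It permits follow-up to five years and panel re-review, describes sampling of adjacent imaging-negative nodes at surgery, and lets clinical follow-up prove disease. It also says that denominators may differ. All of this reduces the bias. It does not remove it, because follow-up is optional and no criterion turns later progression into a baseline miss.

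The exclusion itself is inferred from the sentence on differing numbers and is not written as a rule. That is fair, and the missing rule is part of what needs fixing.

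Three stronger readings are tempting but not supported:

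- **Double-negative men cannot be settled, because they enter on a raised PSA and item 4 requires a stable one.** Item 6 also accepts a PSA fall after bed therapy and/or stable CT or MRI. About 23 of 25 men are expected to have bed disease, and item 7 allows local therapy for men positive in the bed only. Many double-negative men will therefore stay in the analysis as negatives.
- **Every measure is biased upward.** Steps 4 and 5 show that PET sensitivity can reverse and NPV can go either way.
- **A formal relative-rate test among scan-positive men solves the problem.** It needs truth settled equally across those cells, which the anatomic-target condition does not promise. It would also rest on about 4 discordant men, whereas an exact two-sided paired test cannot reach 0.05 with fewer than 6 (five all one way gives 2/32 = 0.06).

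Finally, in so small a trial sampling error is large: the exact 95% interval for 7/9 is about 40% to 97%. That argues for modest emphasis. But the interval does not allow for lost misses, so it cannot stand in for bounds.

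**Conclusion.** The point holds as a matter of expected direction. Complete-case extraprostatic sensitivity is expected to be overstated for either scan positive and for MR. For PET alone the usual direction is upward, but it can shrink or reverse if PET-only-positive men without an anatomic target also go unsettled. NPV rises if missed nodes are called negative and falls if double-negative men are simply dropped.

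This rests on two conditions: at least one node is missed by both scans, and such nodes are settled as positive less often than nodes seen on a scan. The first is likely under the sensitivities tried above. The second follows from C1.7. The size cannot be computed from the documents, and the figures above are illustrations under stated assumptions. With about 9 node-positive men, each lost miss moves sensitivity by roughly 10 percentage points or more. This should be changed. It does not call the conduct of the trial into question.

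**What to change.** - **State the rule.** Keep all 25 men in the extraprostatic table. Give the number with unsettled truth in each of the four PET/MR result cells, including scan-positive men who were not sampled.
- **Report bounds.** Give sensitivity, specificity, PPV and NPV complete-case, then with unsettled men all counted as diseased, then all as disease-free. For example, 7 of 9 settled positives detected, plus 3 unsettled men negative on the scan in question, gives 7/9 = 78% and 7/12 = 58%. The second is an extreme, since it implies 12/25 = 48% node-positive. Where unsettled men are both positive and negative on a scan, mixed allocations can fall outside these two extremes, and the cell counts let a reader work them out.
- **Limit the PET/MR ratio.** The ratio of true-positive rates among men positive on at least one scan may be given as a descriptive supplement only, with its equal-settling assumption stated.
- **Reconcile the absence criteria.** C1.7 item 4 asks for no nodal progression and stable PSA. Item 6 asks for at least 6 months of PSA response and/or more than a year of stable imaging. E.1 gives at least 1 year for NPV and at least 6 months for truth of absence. Say also when later nodal progression makes the baseline scan a false negative.

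The cost is a little more analysis and wider reported ranges. No extra procedure is needed.
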